8.3.4 Questionnaires

Participants will be asked to complete several questionnaires during the screening visit and the test day. These questionnaires will be completed in a secure electronic environment, named Castor, accessible via the Internet through a telephone or computer. Castor was developed by the Maastricht Center and Information and Data Management (MEMIC), affiliated with Maastricht University. Castor utilizes a NEN7510 and ISO 27001:2005 certified server called “True”. Our research group

has previously used Castor in the “FORTITUTE” study (NL67607.068.18/METC 18-037) and the “RESILIENCE” study (NL84720.068.23/METC 23-032).

Baseline characteristics questionnaire

‘F1.1_Baseline_Characteristics_Questionnaire_Versie2.0_dd 26-03-2025’

At visit 1, participants will complete this questionnaire concerning baseline characteristics, demographics, lifestyle, and comorbidities.

Generalized Anxiety Disorder 7-Item Scale (GAD-7)

‘F1.2_GAD7_Versie1.0_dd 10-10-2024’

The GAD-7 is a validated 7-item questionnaire, which has been demonstrated to be an efficient tool for screening generalized anxiety disorder and assessing its severity in clinical practice and research (51). It includes seven anxiety symptoms, with cut-off levels for mild, moderate, and severe anxiety. Participants will be asked to complete the GAD-7 during the first visit to screen for anxiety.

Patient Health Questionnaire (PHQ-9)

‘F1.3_PHQ9_Versie1.0_dd 10-10-2024’

The PHQ-9 is a validated instrument utilized for screening, diagnosis, and measuring the severity of depression. It evaluates each of the nine DSM-IV criteria for depression along with key symptoms of major depressive disorder, condensing them into a concise self-report questionnaire. The questionnaire establishes cut-off points for mild, moderate, moderately severe, and severe depression (52). During the initial visit, participants will complete the PHQ-9 to assess for the presence of depression.

The Big Five Inventory (BFI)

‘F1.4_BFI_Versie1.0_dd 10-10-2024’

The BFI is an instrument designed to assess the personality of individuals aged 18 and above. It comprises 44 items divided into five sub-scales, each representing one of the five personality factors: extraversion (8 items), neuroticism (8 items), conscientiousness (9 items), agreeableness (9 items), and openness to experience (10 items). Participants are required to rate the extent to which they agree with the statement using a 5-point Likert scale ranging from 1 (Disagree strongly) to 5 (Agree strongly) (53). During the initial visit, participants will complete the BFI to evaluate their personality traits.

0-10 Visual Analogue Scale (VAS) – Nausea**‘F1.5_VAS_Scales_Versie1.0_dd 10-10-2024’**

Participants will be requested to assess the severity of nausea at regular time intervals following nausea induction and either taVNS or sham stimulation. The score will range from 0 to 100, where 0 indicates ‘no nausea’ and 100 indicates ‘the worst nausea imaginable’. In total, 14 questionnaires will be completed: one at baseline (pre-infusion), one immediately after stopping the lipid infusion (when the predetermined nausea score of 50/100 is reached), at six time points during stimulation at 5-minute intervals, and at six time points in the post-stimulation phase at 5-minute intervals.

0-10 Visual Analogue Scale (VAS) – Other gastrointestinal symptoms**‘F1.5_VAS_Scales_Versie1.0_dd 10-10-2024’**

Participants will be asked to assess the severity of additional gastrointestinal symptoms, including abdominal pain, bloating, and fullness. They will provide a score ranging from 0 to 100, where 0 indicates ‘not at all’ and 100 indicates ‘extremely severe’. These symptoms will be evaluated at the same 14 time points as for nausea severity.

0-10 Visual Analogue Scale (VAS) – The desire to eat**‘F1.5_VAS_Scales_Versie1.0_dd 10-10-2024’**

Participants will be asked to assess their desire to eat by providing a score on a scale from 0 to 100, where 0 indicates ‘no desire to eat at all’ and 100 indicates ‘extremely strong desire to eat’. This will be evaluated at four time points: at baseline (pre-infusion), immediately after stopping the lipid infusion, after taVNS or sham stimulation, and at the end of the post-stimulation period.

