2.2 Secondary Objectives

1. To assess the effect of taVNS on other gastrointestinal symptoms, such as bloating, abdominal pain, and fullness, following intragastric lipid infusion, compared to sham stimulation.

Hypothesis: We hypothesize that taVNS will lead to a significant reduction in other gastrointestinal symptoms, such as bloating, abdominal pain, and fullness, compared to sham stimulation, as measured by a 0-100 Visual Analogue Scale (VAS) score at regular time intervals.

2. To explore the effects of taVNS on the desire to eat following nausea induction, compared to the sham stimulation group.

Hypothesis: We hypothesize that taVNS will lead to an earlier increase in the desire to eat following nausea induction compared to sham stimulation, as measured by a 0-100 Visual Analogue Scale (VAS) at regular time intervals.

3. To investigate the effect of taVNS on plasma levels of ghrelin and motilin following nausea induction.

Hypothesis: We hypothesize that nausea induction will result in a reduction in plasma levels of ghrelin and motilin, and that this reduction will be counteracted by taVNS.

4. To investigate the effects of taVNS on salivary cortisol levels following nausea induction.

Hypothesis: We hypothesize that nausea induction will result in an increase in salivary cortisol levels, and that this increase will be attenuated by taVNS.

5. To evaluate how affective symptoms and personality traits, utilizing the GAD-7, PHQ-9, and BFI, influence the nausea response.

Hypothesis: We hypothesize that affective symptoms, such as anxiety, and personality traits will modify the nausea response.

6. To evaluate the effect of taVNS on parameters related to autonomic outflow, using a Fitbit smartwatch for heart rate variability (HRV), and a Shimmer3 GSR sensor for HRV and skin conductance.

Hypothesis: We hypothesize that treatment with taVNS will lead to significant changes in the autonomic outflow reflective of an increase in parasympathetic activity.

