The lipid infusion will be immediately halted if the participant's nausea score reaches the 50/100 threshold or if they begin retching. This is to prevent excessive discomfort. Any signs of severe nausea, such as vomiting or a participant's request to stop the procedure, will also lead to immediate cessation of the infusion.

After stopping the infusion, the nasogastric tube will be promptly removed, and participants will then receive either taVNS or sham stimulation for 30 minutes. During this stimulation phase, the severity of nausea will be assessed using a 0-100 VAS score, where 0 signifies "no nausea" and 100 represents "the worst nausea imaginable". VAS scores will be recorded every 5 minutes, continuing for 30 minutes post-stimulation to evaluate the efficacy of taVNS in alleviating nausea. VAS scores

for other gastrointestinal symptoms will also be recorded at the same time points as nausea severity. Additionally, VAS scores for the desire to eat will be recorded at four specific time intervals.

Plasma levels of ghrelin and motilin and salivary cortisol will be measured on four different time points: baseline, at the end of nausea induction, immediately after the taVNS vs. sham stimulation, and 60-minutes post-nausea induction.

Autonomic parameters, including heart rate variability and skin conductance, will be continuously recorded from the onset of nausea induction until 30 minutes after either taVNS or sham stimulation. These measurements will be captured using a Shimmer3 GSR sensor and Fitbit smartwatch, as was previously utilized in other studies within our department (NL87188.068.24/METC 24-029). The Shimmer3 GSR sensor, a CE-certified device (see K6.6_Shimmer_CE_Certificate_of_conformity_Versie1.0_dd 04-09-2014) will be used to collect data on heart rate variability and skin conductance. The Fitbit wearable device will be used to collect participant data concerning HRV. The device will be connected to the coordinating investigator's smartphone via Bluetooth and the Fitbit app. Heart rate data will then be automatically collected by the Fitbit.

Once all measurements are completed, the tVNS device, intravenous cannula, Shimmer, and Fitbit will be removed.

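### Secondary objective 2 predicts an earlier rise in desire to eat, but the schedule places any rise only to within about 30 minutes

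*Protocol*

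**What the plan says.** Secondary objective 2 (Protocol 2.2) is worded as exploratory: "To explore the effects of taVNS on the desire to eat following nausea induction, compared to the sham stimulation group". Its hypothesis is about timing: "We hypothesize that taVNS will lead to an earlier increase in the desire to eat following nausea induction compared to sham stimulation". The same sentence says that the VAS will be taken at regular intervals.

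The schedule is in two places. Section 8.3.2 says "VAS scores for the desire to eat will be recorded at four specific time intervals". Section 8.3.4 lists the first three as follows: "This will be evaluated at four time points: at baseline (pre-infusion), immediately after stopping the lipid infusion, after taVNS or sham stimulation". The fourth reading comes when the follow-up after stimulation closes. The phase lengths come from section 8.3.2: "participants will then receive either taVNS or sham stimulation for 30 minutes" and "VAS scores will be recorded every 5 minutes, continuing for 30 minutes post-stimulation".

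For nausea, section 8.3.4 plans 14 readings: baseline, infusion stop, then "at six time points during stimulation at 5-minute intervals, and at six time points in the post-stimulation phase at 5-minute intervals". Abdominal pain, bloating and fullness follow the same 14 points. All the VAS items cite the same form, F1.5.

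Section 8.1.2 names the endpoint as changes in desire to eat. Section 10.2 analyses the scores with a linear mixed-effects model, as for the primary outcome.

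**The concern.** The hypothesis concerns when desire to eat comes back, and the schedule says little about when. Baseline and infusion stop both precede stimulation. They give a reference level but cannot show a treatment effect on timing. That leaves one reading at the end of stimulation and one at the end of follow-up.

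The other VAS symptoms are recorded every 5 minutes in the same hour, while desire to eat is left off that grid. The number of readings is a design feature fixed in the protocol, and no later analysis can recover readings that were never taken. At stake is how far secondary objective 2 can be answered as worded.

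**Working it through.** **1. The protocol's own figure.** It gives no sample size or power for desire to eat. The only figure is the total of 26 for nausea (section 4.4: difference 25 mm, SD 21.5, two-sided alpha 0.05, power 0.80, 1:1). The noncentral t calculation gives power 0.777 with 12 per arm and 0.812 with 13 per arm, so 2 × 13 = 26 reproduces. The check below uses 13 per arm.

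**2. Readings after treatment starts**, with time 0 at infusion stop and the short gap for tube removal ignored:

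| Outcome | Readings after start | Times (min) | Spacing |
|---|---|---|---|
| Nausea, pain, bloating, fullness | 6 + 6 = 12 | 5, 10, …, 60 | 5 min |
| Desire to eat | 2 | 30, 60 | 30 min |

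**3. What two readings can locate.** A first rise falls in (0, 30], (30, 60] or after 60 minutes. Rises at 5 and at 28 minutes both first appear at the 30-minute reading, so that 23-minute difference leaves no trace in timing. A shift that crosses 30 or 60 minutes does show.

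**4. Earlier versus larger.** Suppose that desire to eat rises linearly at slope *b* from onset τ under sham, with τ at or before 30 minutes. If taVNS only moves onset earlier by *s*, the group difference is *b·s* at both 30 and 60 minutes. If taVNS instead raises the level by *h* = *b·s* soon after stimulation starts, with no change in the onset of the underlying rise, the differences at 30 and 60 minutes are the same. A model fitted to those two readings cannot tell the two apart. Readings every 5 minutes can, because the paths differ before 30 minutes.

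**5. Illustrative power.** The protocol gives no onset times or SDs, so all of these are assumptions: normal onset times (minimum 1 minute), 13 per arm, two-sided Mann-Whitney test at 0.05 on the first reading at or after onset, 4,000 runs per setting. The simulation standard error is at most √(0.25/4000) ≈ 0.008. Cells show power on the 5-minute grid versus readings at 30 and 60 minutes.

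| Sham onset (min) | taVNS earlier by (min) | SD 8 | SD 12 |
|---|---|---|---|
| 25 | 10 | 0.83 vs 0.34 | 0.50 vs 0.29 |
| 25 | 15 | 0.99 vs 0.44 | 0.83 vs 0.47 |
| 35 | 10 | 0.84 vs 0.65 | 0.51 vs 0.37 |
| 35 | 15 | 0.99 vs 0.94 | 0.84 vs 0.66 |
| 45 | 10 | 0.84 vs 0.39 | 0.49 vs 0.33 |
| 45 | 15 | 0.99 vs 0.87 | 0.83 vs 0.65 |
| 45 | 30 | 1.00 vs 1.00 | 1.00 vs 1.00 |
| 55 | 10 | 0.83 vs 0.40 | 0.49 vs 0.34 |
| 55 | 20 | 1.00 vs 0.91 | 0.97 vs 0.89 |

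Power on the current schedule runs from 0.29 to 1.00, against 0.49 to 1.00 on the 5-minute grid. The loss depends mainly on where the two onset times lie relative to the 30- and 60-minute readings.

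**The case against.** **The schedule still carries timing information.** A reader might infer that an earlier rise cannot be detected at all, or that objective 2 cannot be answered. The protocol does not support that. With a reference reading at infusion stop, a taVNS advantage at 30 minutes that closes by 60 minutes would be direct, if coarse, evidence of an earlier rise. The table shows useful power in several settings. This objection stands: the limit is one of resolution.

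**Desire to eat is not the only outcome with a time element.** A reader might infer that the one timing outcome was left off the grid. The primary hypothesis (section 2.1) and primary endpoint (section 8.1.1) also cover the duration of nausea, which is on the grid.

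**The power figures belong to another analysis.** They use a rank test on first rise, an event that the protocol does not define, while section 10.2 plans a mixed model on scores. No power was computed for that model on either schedule, so the table illustrates lost resolution and does not estimate the trial's own loss. How *earlier* would be derived from the scores is something an analysis plan may settle, and is not counted here.

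**The harshest setting may be unrealistic.** Sham onset at 25 minutes with a 15-minute shift puts mean taVNS onset at 10 minutes. With SD 12, a share of Φ(−10/12) ≈ 20% would recover appetite before the infusion stops. The expected fat load is large (258 ml × 22.5/5 kcal per ml ≈ 1,161 kcal), and section 8.3.2 expects nausea to subside gradually. Later onset often costs less, but a 10-minute shift still loses noticeably at sham onsets of 45 and 55 minutes.

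**The four points are not arbitrary.** They match the blood and saliva sampling times (section 8.3.3), and section 3 links ghrelin to appetite. The protocol does not give this as the reason, and keeping those four points does not rule out adding others.

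**Conclusion.** The mismatch is real and modest. The hypothesis is about timing, and the schedule resolves timing to about 30 minutes where the neighbouring symptoms get 5. Shifts inside one interval cannot be seen, and higher scores at both readings do not distinguish earlier from larger.

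The 30- and 60-minute times follow from the stated phase lengths. The size in power terms is conditional on assumed onset times, SDs and a first-rise rank test: no loss for a 30-minute shift, and roughly half for a 15-minute shift with sham onset near 25 minutes (0.99 to 0.44 with SD 8, 0.83 to 0.47 with SD 12).

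This is one of six secondary objectives and is worded as exploratory. The primary comparison and the total of 26 are untouched. It is worth correcting because it is cheap before data are collected and cannot be repaired afterwards.

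**What to change.** Score desire to eat at the 14 time points already used for nausea and the other symptoms. Keep the mixed model, with a group-by-time contrast on that grid, and amend sections 8.3.2 and 8.3.4 to match. The four present readings are among the 14, so this adds 14 − 4 = 10 readings. Each is one more VAS line when participants already complete four (nausea, pain, bloating, fullness). The cost is slight extra participant burden, with no added staff, visit or procedure.

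If the sponsor prefers to keep four readings, reword the hypothesis in section 2.2 as a higher desire-to-eat score under taVNS at 30 and/or 60 minutes after the infusion stops. That costs only a text change, but gives up the claim about timing. Either way, sections 2.2, 8.3.2 and 8.3.4 should agree.

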8.4 Withdrawal of individual subjects

Subjects can leave the study at any time for any reason if they wish to do so without any consequences. The investigator can decide to withdraw a subject from the study for urgent medical reasons.

8.5 Replacement of individual subjects after withdrawal

We accounted for potential dropouts in our sample size calculation.

If a subject decides to discontinue participation before completing all study procedures, this subject will be considered a dropout and will be excluded from analyses. In case this happens during the recruitment period of the study,

researchers may choose to replace the subject. However, subject IDs will not be reused to prevent data confusion; instead, a new subject ID will be assigned to the “replacing” participant.

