4.4 Sample size calculation

Our primary outcome of interest is a reduction in nausea, as measured by visual analogue scales (VAS). Currently, no directly comparable studies are available for an accurate sample size calculation, as previous research has not examined the effect of tVNS on nausea severity in healthy participants using VAS scores. However, a randomized controlled trial in patients with chronic nausea and vomiting due to gastroparesis or gastroparesis-like syndrome evaluated nausea improvement after either aprepitant or placebo treatment (23). This study indicated that a reduction in the mean 28-day VAS score from baseline of at least 25 mm was considered a responder. A standard deviation of 21.5 was noted in the treatment group.

The sample size calculation was based on an unpaired-sample t-test (taVNS vs. sham stimulation) with a mean difference of 25 mm and a standard deviation of 21.5. The following parameters were applied: a significance level (alpha) of 0.05 (two-sided) and a power of 0.80. Based on this calculation, we determined that 26 participants are needed. Because non-responders to nausea induction can occur, we will continue enrolment until 26 participants who meet the responder definition for nausea induction (VAS = 50 during induction) have completed the protocol. The calculation can be found at the following web address:

<https://homepage.univie.ac.at/robin.ristl/samplesize.php?test=ttest>

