5.1.2 Sham stimulation

In the control group, sham stimulation will be administered to the same electrode location (left cymba conchae) using an identical device as that used for taVNS. The electrode used for sham stimulation will be non-conducting, ensuring that there is no stimulation of the vagus nerve. Although the devices for tVNS and sham stimulation appear identical, the electrodes for each group are slightly different. Consequently, the investigator responsible for programming the devices will be aware of the treatment allocation. Participants will not be aware of the treatment received since stimulation is provided to the same location, and the device will still blink during both types of stimulation to maintain blinding (28). The randomization code will be altered

before analysis, ensuring that the investigator conducting the data analysis remains unaware of the treatment allocation. The randomization code will be kept confidential until after the modified intention-to-treat analysis has been reported.

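### Section 8.5 claims a dropout allowance that the Section 4.4 calculation does not contain, and its optional replacement and exclusion rules conflict with Sections 4.1, 4.4 and 10

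*Protocol*

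**What the plan says.** **The calculation (Protocol 4.4).** The inputs are an unpaired t-test of taVNS against sham "with a mean difference of 25 mm and a standard deviation of 21.5", two-sided alpha 0.05 and power 0.80. The result: "Based on this calculation, we determined that 26 participants are needed". No dropout rate and no inflation factor are given.

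**The enrolment rule (Protocol 4.4, also Summary and 4.1).** Prompted by possible non-response to the lipid infusion, 4.4 adds that "we will continue enrolment until 26 participants who meet the responder definition for nausea induction" have completed the protocol. The Summary and 4.1 give the same stopping point.

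**The dropout rule (Protocol 8.5).** The section opens with "We accounted for potential dropouts in our sample size calculation". It then defines a dropout as someone who stops before finishing all study procedures, removes that person from the analyses, and says that, if this happens during recruitment, "researchers may choose to replace the subject".

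**The analysis set (Protocol 10 and 10.1).** The modified intention-to-treat set holds every randomised participant who gets through the induction and in whom stimulation is started. Completing the session is not required. The linear mixed model is to use whatever data each person has, without dropping people who have gaps.

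**The concern.** Section 8.5 is where site staff will look when someone leaves. It tells them that losses are already provided for and that making a loss good is a choice. Section 4.4 shows no such provision in the calculation and leaves no choice. Both rules apply to an induction responder who leaves before finishing, and they give different answers on whether enrolment must continue.

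The same paragraph of 8.5 also takes a dropout out of the analyses, whereas Section 10 keeps that person if stimulation had begun. So the protocol does not settle either how many completers it must reach or who is analysed. At stake are a sample-size statement that is wrong as written, a power that depends on which section is followed, and an analysis set that could be defined by completing the session and not by starting treatment.

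**Working it through.** **Inputs, all from Protocol 4.4 except the last.** Difference 25 mm; SD 21.5; two-sided alpha 0.05; target power 0.80; total 26; allocation 1:1 (Sections 3 and 8.2), so 13 per arm if the split is even.

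**Step 1. Reproduce the 26.** Standardised difference d = 25 / 21.5 = 1.163. For arms of size n1 and n2, the t statistic has n1 + n2 − 2 degrees of freedom and noncentrality

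δ = 25 / (21.5 × √(1/n1 + 1/n2)).

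Power is the probability that a noncentral t with that δ falls beyond the two-sided 5% critical value.

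- 13 + 13: δ = 1.163 × √(13 × 13 / 26) = 2.965, critical value 2.064 on 24 df, power 81.2%.
- 12 + 12: δ = 1.163 × √(12 × 12 / 24) = 2.848, critical value 2.074 on 22 df, power 77.7%.

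The smallest balanced total that reaches 80% is therefore 26. The protocol's figure reproduces exactly, and rounding up to whole, equal arms leaves 1.2 points above target. There is no arithmetic error and no dropout inflation inside the 26.

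**Step 2. What an allowance would have looked like.** The protocol gives no dropout rate, so these rates are assumptions. Dividing 26 by (1 − rate) and rounding up gives:

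| Assumed dropout | Total needed for 26 evaluable |
|---|---|
| 5% | 28 |
| 10% | 29 |
| 15% | 31 |
| 20% | 33 |

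None of these totals is in the protocol.

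**Step 3. Power if 8.5 is followed**, that is, the loss is not replaced and the person is not analysed:

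| Losses | Arms | Power |
|---|---|---|
| 0 | 13 + 13 | 81.2% |
| 1 | 13 + 12 | 79.4% |
| 2 | 12 + 12 | 77.7% |
| 2 | 13 + 11 | 77.4% |
| 3 | 12 + 11 | 75.7% |
| 4 | 11 + 11 | 73.7% |

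One loss ends 0.6 points below 80% (80.0 − 79.4). Two losses end about 2.5 points below.

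**Step 4. Power if 4.1 and 4.4 are followed.** A dropout never counts toward the 26, so completers stay at 26 and power at 81.2% for an even split.

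**Step 5. The exclusion clause against the analysis set.** Take a participant who reaches the induction threshold, starts stimulation and leaves part-way. Under 8.5 this person is out of the analyses. Under Section 10 this person is in the modified intention-to-treat set, and under 10.1 the recorded scores enter the mixed model. The two cannot both be applied. Under the Section 10 reading, the power losses in step 3 are upper limits for dropouts of this kind, because their partial data still count.

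**The case against.** The strongest reply is that the plan does protect itself. Section 4.4, whose heading is the sample size calculation, contains the completer rule, and the Summary and 4.1 repeat it. The protocol also uses the word drop-out for induction non-responders (5.2.1 and 8.3.2), whom 4.4 expressly provides for. On that reading the opening sentence of 8.5 is loose wording for continued enrolment, not a promise of a numerical margin. This largely stands as an account of what was meant. It does not make the sentence accurate: 8.5 goes on to define a dropout as someone who discontinues, and nothing in the calculation allows for that.

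The second reply is that the exposure is small. There is one test day of about three hours, Section 10 expects no missing data, and a single loss costs less than the uncertainty in the SD, which comes from a drug trial in patients with gastroparesis or a similar syndrome: at 13 + 12 an SD of 21.3 already gives 80.2%. This stands. The recruitment-period limit also has little practical force while enrolment stays open to 26 completers.

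Two stronger readings are tempting and are not supported:

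- **That the trial is underpowered, or loses its 80% in any meaningful way with one dropout.** The loss needs 8.5 to override three statements of the completer rule, and needs the exclusion to override Section 10. One loss is then nominal.
- **That knowledge of allocation will steer replacement.** Section 5.1.2 does say that "the investigator responsible for programming the devices will be aware of the treatment allocation", but no section says that this person decides on replacement, or that a replacement takes the dropout's arm. An automatic rule is still preferable because the question then cannot arise.

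**Conclusion.** The point holds as an inconsistency within the protocol. The statement in 8.5 about the sample size calculation is not true of the calculation shown: 26 is the uninflated t-test number. Optional replacement in 8.5 contradicts enrolment to 26 completers in the Summary, 4.1 and 4.4. The exclusion of dropouts in 8.5 contradicts the analysis set in Section 10 and the use of all available data in 10.1.

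The numerical effect is modest and conditional: 79.4% after one unreplaced and excluded loss, about 77.5% after two, and no loss if the completer rule governs. These figures rest on the protocol's own difference and SD, an even split of completers between arms, and t-test power as in 4.4; the primary analysis is a mixed model, whose power the protocol does not calculate. The change is worth making because it corrects a stated property of the sample size and costs almost nothing.

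**What to change.** Edit Section 8.5 in three places.

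1. **Dropout sentence.** Delete it, or replace it with a statement that the 26 in Section 4.4 holds no numerical allowance for dropouts and that losses are covered by continued enrolment.
2. **Replacement.** Replace the discretionary wording with the rule in 4.1 and 4.4: enrolment continues automatically until 26 induction responders have completed, regardless of the arm in which a loss occurred. Each further participant gets a new ID, as 8.5 already says, and is randomised in the normal sequence.
3. **Exclusion.** Replace the blanket removal of dropouts with a reference to Section 10: participants in whom stimulation was started stay in the modified intention-to-treat analysis with the data they provided; those who leave before that point are outside the set by its own definition.

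The cost is a few sentences, to be notified to the ethics committee as an amendment if the protocol already has its favourable opinion. No participants are needed beyond those that 4.4 already commits to, and no new analysis is needed. One consequence should be stated openly: the analysed set may slightly exceed 26, because partial completers are kept alongside the 26 who finish.
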